Product Description	
The Selective Cytopheretic Device (SCD) is comprised of tubing, connectors, and a synthetic membrane cartridge. The device is connected in series to a commercially available Continuous Renal Replacement Therapy (CRRT) device. Blood from the CRRT circuit is diverted after the CRRT hemofilter through to the extra capillary space (ECS) of the SCD. Blood circulates through this space and it is returned to the patient via the venous return line of the CRRT circuit. Regional citrate anticoagulation is used for the entire CRRT and SCD blood circuits.
 
The SCD █ is a synthetic membrane with the ability to bind activated leukocytes and when used in a continuous renal replacement extracorporeal circuit in the presence of regional citrate anticoagulation modulates inflammation.

Rationale	
Our primary hypothesis is that up to seven sequential 24-hour SCD treatments will improve survival in pediatric patients with Acute Kidney Injury (AKI) as compared to CRRT alone (standard of care). Further, SCD therapy will reduce the duration of maintenance dialysis secondary to AKI due to acute tubular necrosis (ATN). ATN is an acute reversible process and if not reversed in three months, it may not be reversed at all. [1, 2] Studies suggest that approximately 10-20% of AKI patients do not recover renal function [3, 4] and, therefore, require chronic dialysis.
 
Importantly, acute kidney injury is a highly lethal condition in critically ill patients. Despite improvements in acute medical care and advances in dialysis therapies, the mortality rate during the past four decades of this condition has not improved. Critically ill patients with AKI in hospital ICU settings have mortality rates of approximately 50%, including pediatric patients [5, 6, 7, 8, 9, 10, 11, 12]
 
AKI promotes a systemic inflammatory response syndrome (SIRS) which results in systemic microvascular damage and, if severe, multi-organ dysfunction. [13, 14] Activated circulating leukocytes play a central role in this process. [15] Leukocytes,

	especially neutrophils, are major contributors to the pathogenesis and progression of many inflammatory disorders, including SIRS, sepsis, ischemia reperfusion injury, and acute respiratory distress syndrome (ARDS). Many therapeutic approaches are under investigation to limit the activation and tissue accumulation of leukocytes at sites of inflammation to minimize tissue destruction and disease progression. [16, 17, 18]
Primary Objective	To evaluate the safety of the SCD treatment up to seven consecutive 24 hour SCD treatments in the pediatric AKI population being treated with Continuous Renal Replacement Therapy (CVVH, CVVHD, or CVVHDF) with regional citrate anticoagulation.
Secondary Objective	To evaluate the effect of up to seven consecutive 24 hour SCD treatments on all cause mortality and dialysis dependency at day 28, and day 60 in the pediatric AKI population being treated with Continuous Renal Replacement Therapy (CVVH, CVVHD, or CVVHDF) with regional citrate anticoagulation. These outcomes will be compared to a historical data set.
Study Endpoints	In this Pilot study four domains of interest have been designated. The four domains are: 
 Patient Safety: Safety Endpoint Measures include adverse events, laboratory safety parameters, vital signs, EKG, ventilation status and hemodynamic variables. Clinical Efficacy: The Primary Clinical Efficacy Endpoint Measure is in-hospital; 28 and 60-day all-cause mortality. Time to renal recovery and necessity for chronic dialysis up to day 60 will also be determined. Additional efficacy endpoints include time to intensive care unit (ICU) discharge, and time to hospital discharge. Device Integrity and Performance: The Endpoint Measure is SCD use without failure. This measure will help assess the integrity and performance of the SCD device. SCD Mode of Action: Exploratory Endpoint Measures will include inflammatory cytokines, cell activation parameters and biomarkers at clinical sites with this capability.
Assessment of Device Integrity and Performance	Criteria for assessment of device integrity and performance include: 
 Significant Clotting within the Device as assessed by visual inspection. Evidence of leakage (i.e., cracking/breakage of a port, connector, hemofilter cartridge or tubing). Any unforeseen malfunction that results in the need for

	discontinuation.
Study Populations	Pediatric patients with a body weight (BW) greater than or equal to 15 kg receiving care in the Intensive Care Units of each participating hospital will be screened daily and identified for participation in the trial.
Study Design	This is an open-label, multi-center Pilot study.
Approximate Number of Subjects	Up to 30 patients will be enrolled in this study.
Approximate Number of Centers	Up to 10 Clinical Centers in the United States will participate in this study.
Duration of Subject Participation	Each patient will be followed for 60 days following enrollment.
Inclusion Criteria	
 1. A patient, or legal representative, has signed a written informed consent form. 2. Must be receiving medical care in an intensive care unit (e.g., PICU, MICU, SICU, CTICU, Trauma). 3. Age less than 22 years. 4. Females of child bearing potential who are not pregnant (confirmed by a negative serum pregnancy test) and not lactating if recently post-partum. 5. Intent to deliver full supportive care through aggressive management utilizing all available therapies for a minimum of 96 hours. 6. Clinical diagnosis of AKI due to etiologies requiring CRRT (see Appendix B). AKI is defined as acute kidney injury with any one of the following: 
 • Increase in SCr by ≥ 0.3 mg/dL (≥ 26.5 $\mu\text{mol/L}$) within 48 hours or; • Increase in SCr to ≥ 1.5 times baseline, which is known or presumed to have occurred within the prior 7 days or; • Urine volume $<0.5\text{ml/kg/h}$ for 6 hours 7. At least one non-renal organ failure (defined as receiving mechanical ventilation or at least one vasoactive medication to treat hypotension) OR presence (proven or suspected) of sepsis. (Appendix C).

Exclusion Criteria	
 1. Threshold blood pressure of 80/40 mmHg-- patients with both a systolic blood pressure of less than 80 mmHg and a diastolic blood pressure of less than 40 mmHg. 2. Irreversible brain damage based on available historical and clinical information. 3. Patients with a solid organ transplant or those with a bone marrow or stem cell transplant in the previous 100 days or who have not engrafted. 4. Acute or chronic use of circulatory support device other than ECMO such as LVADs, RVADs, BIVADs. 5. Presence of preexisting advanced chronic renal failure (i.e., ESRD) requiring chronic renal replacement therapy prior to this episode of acute kidney injury or with pre-existing chronic kidney disease (CKD) defined as a eGFR<30 ml/min/1.73m². Patients who have never seen a pediatric nephrologist will be assumed not to have pre-existing CKD. 6. AKI occurring in the setting of burns, obstructive uropathy, vasculitis, scleroderma renal crisis, atheroembolism, functional or surgical nephrectomy, cyclosporine, or tacrolimus nephrotoxicity. 7. Received >12 hour of CRRT (not including SCUF on ECMO) during this hospital admission or prior to transfer from an outside hospital. 8. Received >1 hemodialysis treatment during this hospital admission or prior to transfer from an outside hospital. 9. Metastatic malignancy which is actively being treated or may be treated by chemotherapy or radiation during the subsequent three month period after study therapy. 10. Chronic immunosuppression with the exception of corticosteroids up to a dose of 10 mg per day. 11. HIV or AIDS. 12. Severe chronic liver failure as determined by standard diagnostic requirements. 13. Current Do Not Attempt Resuscitation (DNAR), Allow Natural Death (AND), or withdrawal of care status, or anticipated change in status within the next 7 days. 14. Patient not expected to survive 28 days because of an irreversible medical condition. (This is not restrictive to AKI, and may include situations such as the presence of irreversible brain damage, untreatable malignancy, inoperable life threatening condition, or any condition to which therapy is regarded as futile by the PI.) 15. Any medical condition that the Investigator thinks may interfere with the study objectives. 16. Physician refusal.
--------------------	---

	
17. Dry weight of <15 kg.18. Platelet count <15,000/mm³ at time of screening.19. Concurrent enrollment in another interventional clinical trial. Patients enrolled in clinical trials where only measurements and/or samples are taken (NO TEST DEVICE OR TEST DRUG USED) are allowed to participate.20. Use of any other Investigational drug or device within the previous 30 days.
Evaluation Plan	The primary evaluation of this study will be safety and all-cause mortality or dialysis dependency through 60 days post-enrollment. Additional endpoints will be time on CRRT, total ICU and hospital days. Mortality and dialysis dependency rates will be compared to historical controls.

LIST OF ABBREVIATIONS

[figure not shown]
AE	Adverse Event
AKI	Acute Kidney Injury
ARDS	Acute Respiratory Distress Syndrome
ARF	Acute Renal Failure
ATN	Acute Tubular Necrosis
BW	Body Weight
iCa	Ionized Calcium
CBC	Complete Blood Count
CRF	Case Report Form
CRRT	Continuous Renal Replacement Therapy
CTICU	Cardiothoracic Intensive Care Unit
CVVH	Continuous Veno-Venous Hemofiltration
CVVHD	Continuous Veno-Venous Hemodialysis
CVVHDF	Continuous Veno-Venous Hemodiafiltration
ECS	Extra Capillary Space
ICU	Intensive Care Unit
MICU	Medical Intensive Care Unit
nriCa	Non Recommended Ionized Calcium Range
ppCRRT	Prospective Pediatric CRRT Registry
PRISM	Pediatric Risk of Mortality
RAD	Renal Assist Device
riCa	Recommended Ionized Calcium Range
SAE	Serious Adverse Event
SCD	Selective Cytopheretic Device
SICU	Surgical Intensive Care Unit
SIRS	Systemic Inflammatory Response Syndrome
SOFA	Sequential Organ Failure Assessment
WBC	White Blood Cell
UADE	Unanticipated Adverse Device Effect

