2.4 PILOT STUDY USA ARF-002 - IDE [REDACTED]^[22]

2.4.1 STUDY SUMMARY

Acute kidney injury (AKI) is characterized by deterioration in kidney function resulting in multisystem abnormalities. Much of the morbidity and mortality associated with AKI result from a systemic inflammatory response syndrome (SIRS). This study described herein was a prospective, single-arm, multicenter US study designed to evaluate the safety and efficacy of the Selective Cytopheretic Device (SCD) treatment on AKI requiring continuous renal replacement therapy (CRRT) in the ICU. The study enrolled 35 subjects. The mean age was 56.3 ± 15 . With regard to race, 71.4% of the subjects were Caucasian, 22.9% were Black, and 5.7% were Hispanic. Average SOFA score was 11.3 ± 3.6 . Death from any cause at Day 60 was 31.4%. Renal recovery, defined as dialysis independence, was observed in all of the surviving subjects at Day 60. The results of this pilot study indicate the potential for a substantial improvement in patient outcomes over standard of care therapy, which is associated with a greater than 50% 60-day mortality in the literature. The SCD warrants further study in scientifically sound, pivotal trial to demonstrate reasonable assurance of safety and effectiveness.

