3.2 STUDY ENDPOINT

In this Pilot study four (4) domains of interest have been designated. The four (4) domains are:

1. Patient Safety: Safety Endpoint Measures include adverse events, laboratory safety parameters, vital signs, EKG, ventilation status and hemodynamic variables.
2. Clinical Efficacy: The Primary Clinical Efficacy Endpoint Measure is in-hospital; 28 and 60-day all-cause mortality. Time to renal recovery and necessity for chronic dialysis up to day 60 will also be

determined. Additional efficacy endpoints include time to intensive care unit (ICU) discharge, and time to hospital discharge.

3. Device Integrity and Performance: The Endpoint Measure is SCD use without failure. This measure will help assess the integrity and performance of the SCD device.
4. SCD Mode of Action: Exploratory Endpoint Measures will include inflammatory cytokines, cell activation parameters and biomarkers at clinical sites with this capability.

Endpoints are defined in **Appendix D**.

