Besides the test of the hypothesis the study is focused on observable, empirical and laboratory determinations of patient safety while on the SCD. Previous human trials have been conducted on the SCD device and the protocol contains a review of AE and SAE data from all SCD human studies and findings from those studies contributed to constructing the investigative safety profile. Safety endpoint measures specified in the protocol include adverse events, laboratory safety parameters, vital signs, ventilation status and hemodynamic variables. Device integrity and performance measurements are also defined as are circumstances which demand premature termination of SCD treatment.

Prolonged exposure to the SCD is anticipated to result in superior outcomes, although as noted above, this pilot study is not designed to assess for efficacy. However, we understand that a minimum amount of exposure to the SCD will be required for an appropriate safety analysis and for making any inference regarding efficacy. The ppCRRT experience demonstrated that the majority of patients (201/370) received CRRT for 1 to 7 days and exhibited 65% survival (Symons et al CJASN 2007 Table7). Assuming our trial includes patients with similar illness severity, we have established a 72 minimum number of hours a patient will be treated with the SCD to be included in the final outcome analysis.

This trial is an early safety efficacy study but is not powered for statistical significance. Insights into a comparison of historical controls matched to SCD treated patients will utilize the ppCRRT Registry to match for: etiology of AKI, co-morbidities, CRRT modality, dose and form of anticoagulant, adverse events. [10].

The ppCRRT Registry has data fields for the primary reason for CRRT, including AKI and its cause, as well as co-morbidities which will be matched for primary organ system involvement. The CRRT modality was evenly distributed between convective and diffusive modality, with 60% of the convective modalities provided as CVVH and 40% as CVVHDF. The anticoagulant protocol will be standardized with ACD-A/CaCl₂ and all centers used the same protocol in ppCRRT Registry as outlined in this study protocol. Thus, the ppCRRT Registry dataset will be able to be matched to our study patient cohort. Also as noted above, patients will be matched for age, size and PRISM II score.

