APPENDIX D – ENDPOINT DEFINITIONS

ALL-CAUSE MORTALITY:

All cause mortality is defined as in-hospital, 28-day and 60-day all cause mortality.

DIALYSIS DEPENDANCY AT DAY 60:

Dialysis dependency at day 60 is defined as patient not receiving any form of intermittent or continuous renal replacement therapy at or within 3 days of 60 days post enrollment in the study with no plans for additional intermittent or continuous renal replacement therapy.

PATIENT SAFETY:

Adverse events, laboratory safety parameters, vital signs, EKG, ventilation status and hemodynamic variables.

DURATION OF RENAL SUPPORT:

The duration of renal support will be defined as the numbers of days from the initiation of renal replacement therapy (start of observation period) to final dialysis treatment. Duration of renal support will be censored if the patient is still dialysis dependent at the time of death or are dependent at day 60.

RECOVERY OF RENAL FUNCTION:

Recovery of renal function will be defined as lack of need for continuous dialysis support on day 28, and will be classified as yes or no at day 28. Subjects who were alive at day 28 will be included in the analysis. Patients who remain dialysis dependent at study completion (day 60) or time of death will be categorized as having no recovery of renal function.

ASSESSMENT OF SCD █ INTEGRITY AND PERFORMANCE:

The SCD █ will be evaluated for the presence of clotting, leaking or any other malfunction.

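### ICU days, hospital days and time to discharge have no rule for deaths, so with 35–50% expected mortality a survival benefit could be hidden or shown as a longer stay

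*Combined protocol and SAP*

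**What the plan says.** The synopsis, under Evaluation Plan, states: "Additional endpoints will be time on CRRT, total ICU and hospital days". Section 3.2 (and Study Endpoints in the synopsis) words the stay endpoints as times: "Additional efficacy endpoints include time to intensive care unit (ICU) discharge, and time to hospital discharge". Section 3.2 then refers the reader on: "Endpoints are defined in Appendix D".

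Appendix D has no entry for ICU days, hospital days or time to discharge. The only duration it defines is renal support, and that has a death rule: "Duration of renal support will be censored if the patient is still dialysis dependent at the time of death". The rule is not extended to length of stay.

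Death will be common. The synopsis rationale cites "mortality rates of approximately 50%, including pediatric patients". Section 11 reports that most registry patients "received CRRT for 1 to 7 days and exhibited 65% survival", which is 35% mortality. The stated hypothesis is that the device improves survival.

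On comparison with controls, the Evaluation Plan says: "Mortality and dialysis dependency rates will be compared to historical controls". Length of stay is not in that sentence. Section 11 later mentions historical comparisons in general, without listing outcomes.

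**The concern.** Death prevents discharge, and it is the event the device is meant to change. A stay endpoint without a death rule is therefore ambiguous where it matters most. If a death closes the stay, each child saved swaps a stay that ended at death for a full survivor's stay, and the average can rise because the treatment worked. If a death is censored, the analysis describes discharge as though death did not remove patients, and the survival gain disappears from view. Section 11 says the results will inform the design of a pivotal study, so a misleading stay summary could carry forward into that study's endpoints.

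**Working it through.** The documents give no length-of-stay figure, effect size or variance for these endpoints, so there is no stated result to reproduce. The check asks how each possible death rule behaves.

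**Inputs from the documents.** Control mortality m0 is 50% (synopsis rationale) or 35% (100% − 65%, Section 11). Device mortality m1 is 31.4% for illustration, from the adult US pilot in Section 2.4.1 ("Death from any cause at Day 60 was 31.4" per cent). Follow-up is 60 days.

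**Assumptions.** A device mortality of 22% is paired with the 35% control; this is about the same relative reduction (0.35 × 31.4/50 = 0.22). Mean days to death (Td), survivors' mean stay (Ts) and the discharge hazard are also assumed.

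**1. Raw total days, stay ends at death.** Mean stay = m·Td + (1 − m)·Ts. With survivors' stay unchanged, device minus control = (m0 − m1)·(Ts − Td).

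| Td / Ts (days) | 50% vs 31.4% | 35% vs 22% |
|---|---|---|
| 5 / 20 | 12.50 vs 15.29 (+2.79) | 14.75 vs 16.70 (+1.95) |
| 10 / 30 | 20.00 vs 23.72 (+3.72) | 23.00 vs 25.60 (+2.60) |
| 10 / 20 | 15.00 vs 16.86 (+1.86) | 16.50 vs 17.80 (+1.30) |
| 20 / 20 | 20.00 vs 20.00 (0) | 20.00 vs 20.00 (0) |
| 25 / 20 | 22.50 vs 21.57 (−0.93) | 21.75 vs 21.10 (−0.65) |

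First row: 0.50×5 + 0.50×20 = 12.50, and 0.314×5 + 0.686×20 = 15.29. The life-saving device looks 1.3 to 3.7 days worse when deaths precede discharges. There is no difference when the two means are equal, and the sign reverses when deaths come later.

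**2. Offset by a shorter stay in survivors.** The survivors' stay on device that removes the difference is (control mean − m1·Td)/(1 − m1). For 5/20 at 50% vs 31.4% this is (12.50 − 1.57)/0.686 = 15.93 days, 20% shorter than 20. Over the first three rows the break-even is 14–20% shorter (50% vs 31.4%) or 8–12% shorter (35% vs 22%).

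**3. Time to discharge.** Take a constant discharge hazard λ = 1/20 per day in both groups and a death hazard μ = λ·m/(1 − m).

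- Death as end of stay: median = ln 2/(λ + μ), giving 6.9 vs 9.5 days (50% vs 31.4%) and 9.0 vs 10.8 (35% vs 22%). The device looks worse.
- Death censored: median = ln 2/λ = 13.9 vs 13.9 days in both scenarios. The benefit is hidden, not reversed.
- Live discharge by day 60 with death competing: [λ/(λ + μ)]·[1 − exp(−60(λ + μ))], giving 0.50 vs 0.68 and 0.64 vs 0.76. The benefit shows.

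**4. Days alive and out of ICU or hospital to day 60, death = 0.** Mean = (1 − m)·(60 − Ts).

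- Ts = 20: 20.0 vs 27.4 (+7.4) and 26.0 vs 31.2 (+5.2).
- Ts = 30: 15.0 vs 20.6 (+5.6) and 19.5 vs 23.4 (+3.9).

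The direction is right in every case and does not depend on Td.

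**The case against.** A reader might infer that the plan counts an early death as a short stay, so that an effective device would necessarily look worse. The documents do not support that. They name the endpoints and leave death as end of stay, censoring, exclusion and competing event all open. The reversal also needs deaths to precede discharges on average and no sufficient shortening in survivors. The protocol hypothesises shorter dialysis, so some shortening of stay is plausible.

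A reader might also infer that stay will be tested against historical controls. The Evaluation Plan names only mortality and dialysis dependency for that comparison, and the registry factors listed in Section 11 do not include length of stay. In a single-arm study that only describes stay, there is no contrast whose sign can flip. That stands; what remains is an average that mixes deaths with discharges.

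A death on day 3 is a tempting example but a poor one. Section 11 requires at least 72 hours of device treatment for the final outcome analysis, so such a child may not be counted. The rule does not remove the problem. In a simulated example (gamma stays with means of 19.8 days for survivors and 8.3 days for deaths, mortality 50% vs 35%) the apparent lengthening is about 1.7 days. Dropping stays of 3 days or less from both groups still leaves about 1.5.

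The shift is also modest against sampling error. With an assumed SD of 12–13 days, the standard error of a mean is 3.0–3.3 days at the 16 patients of Section 10 (12/√16 to 13/√16) and 2.2–2.4 at the 30 of Section 5.1. These are additional endpoints in an unpowered pilot, no decision rule depends on them, and mortality is reported in the same study. All of this limits the consequence. It does not supply the missing rule.

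**Conclusion.** The gap is real and worth closing. Stay endpoints have no death rule, in a population where about 35–50% may die and where survival is the hypothesised benefit. Raw days, or death as end of stay, could make a life-saving device look about 1 to 4 days worse. Censoring at death, the convention Appendix D uses for renal support, would hide the gain. The size rests on assumed times to death and stays, an adult figure for device mortality, an assumed 22%, and no effect on survivors' stay; with deaths later than discharges the direction changes. The practical harm is greatest if stay is compared with the registry under the general wording of Section 11. The evidence does not show that the plan has adopted a wrong rule, or that the endpoints are bound to mislead.

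**What to change.** Add these entries to Appendix D and align the Evaluation Plan and Section 3.2 with them:

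- **Live ICU discharge, live hospital discharge and end of renal support:** cumulative incidence to day 60 with death as a competing event. For renal support this replaces censoring at death.
- **Total ICU and hospital days:** replace with days alive and out of ICU, and out of hospital, to day 60, with death by day 60 scored 0.
- **Display:** show mortality and survivors' length of stay beside these measures.
- **Historical comparison:** state whether stay will be compared with the registry at all. If so, use the same definitions in both groups and apply the 72-hour minimum consistently.

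The cost is mainly wording. Discharge and renal replacement dates are already collected (Section 6.5.3, Appendix H), and deaths are captured as serious adverse events to day 60 (Sections 9.2 and 9.7.2). One rule has to be added for readmission, because Section 6.5.3 asks for a single ICU and a single hospital discharge date and return to ICU appears only as an example of a serious event. The statistical downside is that free days combine death and stay and so partly repeat the mortality endpoint, which is why the components should be shown as well.

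### Dialysis dependency is compared with historical controls without a denominator or a rule for deaths, so a dependency rate read alone can look better because more children died

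*Combined protocol and SAP*

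**What the plan says.** The Evaluation Plan in the Synopsis contains two readings. It opens with "The primary evaluation of this study will be safety and all-cause mortality or dialysis dependency through 60 days post-enrollment", which could be a composite, and then states "Mortality and dialysis dependency rates will be compared to historical controls", which reads as two separate rates. The Secondary Objective in the Synopsis and Section 3.1 name "all cause mortality and dialysis dependency at day 28, and day 60", again side by side. No section defines a composite.

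Appendix D begins its definition with "Dialysis dependency at day 60 is defined as patient not receiving any form of intermittent or continuous renal replacement therapy" and places the assessment "at or within 3 days of 60 days post enrollment in the study". It gives no denominator and does not mention death. It has no definition of dependency at day 28.

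Death is addressed for two neighbouring endpoints only:
- Recovery of renal function: "Patients who remain dialysis dependent at study completion (day 60) or time of death will be categorized as having no recovery of renal function". The same definition restricts the analysis to subjects alive at day 28.
- Duration of renal support: a patient still on dialysis at death is censored.

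Section 10 plans an efficacy evaluation against historical controls. Section 11 says that the trial was not sized to show significance, and sets 72 hours of SCD treatment as the minimum for entering the final outcome analysis.

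**The concern.** A child who has died has no dialysis status at day 60, and death is expected to be common here. The plan does not say whether such a child counts as dependent, as not dependent, or not at all.

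Both obvious ways of forming a separate rate are distorted by deaths. Over all patients with the dead counted as not dependent, every death adds to the dialysis-free group. Among survivors only, the rate falls when the children who would have stayed on dialysis are the ones who die. In either case the dependency result can improve as survival worsens.

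The controls are external and the scoring is unwritten. It could therefore be chosen after the results are known, or differ between the trial cohort and the registry. Section 11 says that the results will inform the design of a pivotal study.

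**Working it through.** **1. Reproduce the sponsor's figures.** Section 2.5.3 reports SCD-003 patients kept in the recommended calcium range (riCa): 46 evaluable, with 3/19 deaths on SCD and 11/27 on CRRT alone (Table 6). The survivors number 19 − 3 = 16 and 27 − 11 = 16. These are exactly the denominators of Table 8, so the sponsor reported dependency among survivors.

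For a 2×2 table with cells a, b, c, d and total n, the uncorrected Pearson statistic is n(ad − bc)² / (product of the four margins).
- Table 6, 3/19 vs 11/27: 46 × 128² / (19 × 27 × 14 × 32) = 3.279, p = 0.070, as stated.
- Table 8, 0/16 vs 4/16: 32 × 64² / (16 × 16 × 4 × 28) = 4.571, p = 0.0325 (stated 0.033).
- Table 9, 3/19 vs 15/27: 46 × 204² / (19 × 27 × 18 × 28) = 7.404, p = 0.0065 (stated 0.007).

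**2. Change only the scoring of deaths (illustration).**
- Survivors only: 0/16 vs 4/16, 0% vs 25.0%, p = 0.033.
- All patients, dead = not dependent: 0/19 vs 4/27, 0% vs 14.8%; 46 × 76² / (19 × 27 × 4 × 42) = 3.083, p = 0.079.
- Death or dialysis: 3/19 vs 15/27, 15.8% vs 55.6%, p = 0.0065.

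By two-sided Fisher test the three p-values are 0.101, 0.131 and 0.013.

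**3. Direction of the distortion.** Counting the 11 control deaths as dialysis-free cuts the control rate from 25.0% to 14.8%. As a hypothetical, suppose two of the four dialysis-dependent control survivors had died instead. The survivors-only rate would fall from 4/16 = 25.0% to 2/14 = 14.3%. Death or dialysis would stay at 15/27.

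**4. Size in this trial.** Inputs:
- Mortality m = 50% (Synopsis, Rationale), or 1 − 65% = 35% (Section 11, registry patients on CRRT for 1 to 7 days).
- Dependency among survivors d = 10% to 20%. This is an assumption: Section 1.1 gives 10-20% non-recovery among AKI patients and does not say that these are survivors.

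Results:
- All patients, dead = not dependent, (1 − m)d: 0.50 × 0.10 = 5% to 0.65 × 0.20 = 13%.
- Survivors only, d: 10% to 20%.
- Death or dialysis, m + (1 − m)d: 0.35 + 0.065 = 41.5% to 0.50 + 0.10 = 60%.

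At d = 20%, raising mortality from 35% to 50% lowers the all-patient dependency rate from 13% to 10%, while death or dialysis rises from 48% to 60%.

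If the 10-20% refers to all AKI patients instead, the all-patient rate is 10% to 20%. Survivors-only is then 0.10/0.65 = 15% to 0.20/0.50 = 40%, and the composite 45% to 70%. The spread between scorings remains.

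Expected deaths are 10.5 to 15 of 30 (the enrolment ceiling), or 5.6 to 8 of the 16 named in Section 10.

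**5. The wording of the definition.** Read literally, Appendix D calls a patient dependent when renal replacement is not being received. A dead child would then be dependent, the opposite of the dialysis-free scoring above. Separately, dependency taken through 60 days, as the Evaluation Plan words it, would capture every patient, because all are on CRRT at entry.

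**The case against.** The strongest reply is that this is a pilot, not powered and with no stated alpha. All-cause mortality is its primary clinical efficacy measure and will be reported beside dependency, so a fall in dependency caused by deaths would be visible. The Evaluation Plan may already intend a composite through its use of *or*. A composite would also be driven mainly by death (35 of 41.5 points, or 50 of 60), which can hide a renal effect. All of this stands. It argues for keeping a dependency rate as a descriptive result and for showing the components. It does not supply the missing denominator or death rule.

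A reader might infer from the SCD-003 figures that the scoring of deaths alone decides significance. The documents do not support that. The riCa subgroup came from further analysis after the interim look. The crossing of 0.05 between the two dependency-only scorings needs an uncorrected Pearson test on four events, with smallest expected counts of 2 (4 × 16/32) and 1.65 (4 × 19/46). By Fisher test neither scoring is below 0.05, and all three scorings favour SCD.

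A reader might also infer that the plan ignores death entirely. It does not, since recovery and duration have death rules. Those rules conflict and are not applied to dependency.

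**Conclusion.** The concern holds as a defect in a descriptive comparison that the plan commits to. The same outcomes yield about 5-13%, 10-20% or 42-60% depending on unwritten scoring, and a dependency rate read alone can improve because more children died. The ranges rest on the protocol's mortality figures, the lower of which comes from a registry subset with no day-60 horizon stated, and on the assumption that 10-20% of survivors remain dependent. The 72-hour rule may already remove some early deaths, so the number of children left without a score could be smaller than the expected deaths.

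Two stronger conclusions do not follow. The trial is not exposed to a false positive on a planned test, because none is specified. Nor is the composite the only way to give every child a defined outcome, because three exclusive categories also do so.

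**What to change.** - Make death or dialysis dependency at day 60, and at day 28, the main dialysis comparison with the historical controls, with death scored as an event. In the Evaluation Plan, replace the wording that runs through 60 days with status at day 60.
- Report dead, alive on dialysis and alive off dialysis as three exclusive categories at both times. Score the registry controls identically where the registry holds dialysis status at those times. The fields listed in Section 11 do not show that it does, so this needs checking first.
- Keep any dependency-only rate as descriptive, with its denominator and its treatment of deaths stated.
- Correct the inverted definition in Appendix D, add a day-28 definition of dependency, and state how patients lost to follow-up are scored.
- Reconcile the analysis population with the 72-hour minimum in Section 11, and state which patients enter the comparison.

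The cost is wording in the Evaluation Plan, Sections 3 and 11, and Appendix D. The trial cohort needs no new data, since Sections 6.5.2 and 6.5.3 already collect renal replacement status and dates. The downside is a higher headline rate driven mainly by death, so the components must stand beside it.
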